4. ADDITIONAL STUDY CONDITIONS

4.1 IRB Approval

Institutional Review Board (IRB) approval is required for each study site according to local requirements and investigator prior to participation in this clinical study. Subject enrollment may not begin until both the IRB and BIOTRONIK, Inc. have granted approval for the study site. If IRB approval is withdrawn, BIOTRONIK, Inc. must be notified by the investigator within 5 working days.

4.2 Subject Consent

Subject participation in this study is voluntary. All subjects must sign an IRB approved Informed Consent Form (ICF) prior to participation in the study. Subject informed consent must be obtained prior to enrollment or any protocol related procedures. To assist with the consent process, BIOTRONIK, Inc. will provide a template subject ICF to participating sites. Subjects that qualify for the MPP sub-study (Section 11) must sign a separate ICF prior to participating in the MPP sub-study.

4.3 Data Collection

4.3.1 Electronic Data Capture (EDC)

MedNet Solutions Incorporated is a privately-held company that specializes in web-based clinical data management technology. MedNet will host the EDC system and provide a secure environment that is accessible to authorized individuals through the internet. BIOTRONIK, Inc. will implement a study specific configuration using this software to meet the data collection requirements of the protocol. It is the platform for electronic case report form (eCRF) data entry, query management, and access to clinical data for parties authorized by BIOTRONIK, Inc.

4.3.2 Electronic Case Report Forms (eCRFs)

Original data will be collected from each investigational site and recorded into the EDC system via completion of eCRFs. The investigator will be required to use an electronic signature to approve the content of the data reported in the eCRFs. BIOTRONIK, Inc. will audit and monitor the content of the eCRFs as described in Section 9.

Information from electronically delivered source data (e.g. programmers) will be captured and stored in a validated environment until the end of the study.

4.3.3 BIOTRONIK Home Monitoring® Data

In the QP ExCELS study, data of the study subjects will be accessible to the sponsor via transfer from the Home Monitoring Service Center during the course

of study participation of the respective subject. BIOTRONIK Home Monitoring® data might be used for evaluation and publication if desired by the sponsor.

All data are transferred to the sponsor in a pseudonymized form. Data includes all information transmitted from the device (e.g. IEGMs, statistics, lead information).

4.4 Confidentiality of Subject Data

Information sent to BIOTRONIK, Inc. pertaining to study subjects will be kept confidential at BIOTRONIK, Inc. and is subject to audit by IRB and other regulatory authorities. For reporting purposes, data collected from U.S. sites will be shared with BIOTRONIK SE & Co. KG. Information shared with BIOTRONIK SE & Co. KG will be kept confidential. Reports submitted to physicians and data presented in publications of study results will not make any reference to subject name.

In order to verify the study data and ensure study integrity, monitors from BIOTRONIK, Inc., authorized personnel from BIOTRONIK SE & Co. KG, regulatory authorities, and the reviewing IRB may review and/or copy the study records.

4.5 Data Quality Control

BIOTRONIK, Inc. will regularly review study data. At any time, reports can be generated on entered or missing data by BIOTRONIK, Inc. or by approved research personnel at each investigational site. The EDC system will be used to track received and expected visit data and eCRFs for each subject. This system also provides the capability to monitor the status, volume, and disposition of data. In addition, all study data will undergo extensive automatic edit and plausibility checks that provide information to the investigational sites to help improve and maintain data quality control procedures designed to detect inaccuracies and inconsistencies.

4.6 Deviations from Clinical Investigation Plan

The investigator is required to conduct this study in accordance with the signed investigator agreement and clinical protocol. The investigator shall notify BIOTRONIK, Inc. and reviewing IRB in writing no later than 5 working days after any significant deviation from the clinical protocol that has occurred to protect the life or physical well-being of a subject in an emergency. Except in such emergency situations, prior approval by BIOTRONIK, Inc. is required for significant deviations from the clinical protocol.

BIOTRONIK, Inc. categorizes protocol non-compliance instances as either protocol violations or protocol deviations. Both protocol violations and deviations will be reported in the interim and final clinical progress reports.

4.6.1 Protocol Violations

Protocol violations are defined as instances where the protocol requirements and/or regulatory guidelines were not followed, and are generally more serious in nature. Protocol violations are considered to potentially affect the scientific soundness of the study and/or the rights, safety, or welfare of subjects. Protocol violations include, but are not limited to, failure to obtain consent, unapproved investigator implanting an investigational device, and subject inclusion/exclusion violations.

The investigator must notify the reviewing IRB of all protocol violations per the reporting requirements. In some instances, such as failure to obtain consent, the investigator should also seek guidance from the IRB to ensure the subject received appropriate information to consider their participation in the study.

4.6.2 Protocol Deviations

Protocol deviations are defined as instances where the requirements of the protocol were not followed in such a manner whereby data is unusable or unavailable. Protocol deviations are less serious in nature and may not require IRB notification as long as they do not affect the rights, safety, or welfare of the study subject.

4.7 Subject Retention

BIOTRONIK, Inc. will provide additional tools to the sites in an effort to minimize the number of subjects that are lost to follow-up. This includes an overview of each subject's visit schedule, including the windows for each visit as they become due. The visit schedule reporting allows research personnel to become alerted to and track all study subjects that should be scheduled for upcoming study evaluations.

In addition, BIOTRONIK, Inc. monitors will review subjects, including those that may be lost to follow-up, to ensure protocol and study visit compliance.

4.8 Study Completion

BIOTRONIK, Inc. will notify the U.S. study site upon completion or termination of the clinical investigation or of the investigator's participation. BIOTRONIK, Inc. will provide a Clinical Investigation Report to each investigational site. BIOTRONIK, Inc. will also determine which sites will have an on-site close out visit and provide details on closure activities to all investigators to ensure the investigator understands any applicable regulatory requirements, including those related to record retention.

4.9 Labeling and Control of the Investigational Devices

For all sites, the investigational leads and associated components will have a label that will be visible on the pertinent shipping cartons and storage containers. The required labels or manuals will bear the following information:

- Model and serial number of the investigational device (where appropriate)
- Name of the investigational device and the address of BIOTRONIK SE & Co. KG as the manufacturer
- Labeling statement: Caution: Investigational Device. Limited by United States law to investigational use.
- All relevant contraindications, hazards, adverse device effects, interfering substances or devices, warning and precautions.

BIOTRONIK, Inc. will control the investigational devices within the U.S. by distributing those devices only to approved investigational centers and approved investigators. BIOTRONIK, Inc. will also keep records that indicate the place and date of shipment. Devices are not transferrable between investigators unless prior approval is obtained from BIOTRONIK, Inc.

Upon receipt of FDA approval of the Sentus QP lead, this section will no longer be applicable.

5. STUDY OVERSIGHT

5.1 Clinical Events Committee

A Clinical Events Committee (CEC) consisting of at least 3 independent Electrophysiologists or Cardiologists (with CRT experience) will be established to review and adjudicate all protocol defined adverse events reported by the investigational sites related to:

1. Lead or generator adverse event resolved by surgical reposition, surgical explanation, surgical replacement, surgical abandonment, or if other lead-related surgery is performed
2. Adverse event related to clinical lead failure, electrical lead failure, or mechanical lead failure, regardless of action taken. This includes PNS resolved by electrical abandonment and disabled pacing
3. Any major implant procedure related event that meets the criteria of a serious adverse event
4. (MPP Sub-Study Only, see Section 11.3.4) MPP sub-study related events.

Protocol defined adverse events that do not meet these criteria for CEC adjudication (e.g. reprogramming pacing output due to high LV threshold without a suspected or confirmed lead failure) will be included in the clinical report based on site-reported information.

The CEC will be blinded to the investigational site and subject identity, and to minimize bias members will not participate as investigators. The CEC will create a study specific charter defining the adverse event adjudication process, specifically detailing review guidelines along with appropriate response timelines.

Adverse events meeting the criteria described above will be adjudicated by the Clinical Events Committee. The Clinical Events Committee (CEC) will have the responsibility to adjudicate the classification, category, seriousness, and resolution of each reported adverse event. In addition, the CEC will also indicate whether the adverse event is related, possibly related, not related, or has an unknown relation to the Sentus QP lead or Plexa ICD lead. The CEC will decide for each event on the inclusion to the primary endpoint 3 analysis according to the definition for endpoint 3 relevant adverse events as documented in Section 6.6.2.

The Clinical Events Committee is responsible for:

- Endpoint adjudication of adverse events meeting the criteria above
- Adjudication meetings, as needed, via telephone conference or face-to-face
- Final decision on inclusion of each adverse event in the primary endpoint 3 analysis according to the definition provided in Section 6.6.2.
- Regular reporting of adjudication results to the sponsor

The Clinical Events Committee will be supported by members of the sponsor in pre-selection of device complications from non-device related adverse events (e.g. broken leg, headache, cancer) and in organizational tasks.

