3.5.2.4 Subject death

In the event of subject death during study participation, personnel at the investigational site are requested to notify BIOTRONIK, Inc. immediately by completing an Adverse Event eCRF (if applicable) and a Study Termination eCRF.

The following information will be required for any subject death:

- Death certificate, death report signed by the investigator, or relevant medical records that include:
 - Date of death
 - Primary cause of death
 - Any other circumstances surrounding the death
 - Whether death was device or procedure related
- Sentus QP lead return status, if available

Whenever possible, devices that are explanted must be returned to BIOTRONIK, Inc. for analysis.

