6.6 Adverse Events for Primary Endpoint Analysis

The complication-free rate calculated for primary endpoint 1 will be based on the total number of subjects with at least one ADE. For the primary endpoint analysis, the AE classification, category, resolution and relation to the investigational device (Sentus QP lead) for each individual event will be determined by the Clinical Events Committee (CEC) (see Section 5.1).

All adverse events that meet the primary endpoint criteria (Section 6.6.1) and for which the CEC determines the event is related or possibly related to the Sentus QP lead will be included in the primary endpoint event analysis. Adverse events with a final CEC adjudicated relation of not related or unknown will not contribute to or be included in the evaluation of the primary safety endpoint.

6.6.1 Adverse Events Included in Primary Endpoint 1

ADEs related to the Sentus QP lead and resolution combinations that will be analyzed as part of the primary endpoint 1 ($p_{\text{Complication}}^{\text{SentusQP}}$) are presented in Table 7.

Combinations marked with an “X” will be included but are not limited to the primary endpoint 1 analysis. All Sentus QP related ADEs meeting the below criteria occurring after successful implantation until the 6-month post-implantation visit will be included.

Table 7: Adverse Event/Resolution Combinations for Primary Endpoint 1 Analysis

Resolution	Clinical lead failure	Electrical lead failure	High pacing threshold	Extracardiac stimulation	Intermittent capture	Lead dislodgement	Lead impedance out of range, high	Lead impedance out of range, low	Lead undersensing	Lead-related thrombosis	Loss of sensing	Mechanical lead failure	No capture
Lead surgically repositioned	X	X	X	X	X	X	X	X	X	X	X	X	X
Lead surgically explanted	X	X	X	X	X	X	X	X	X	X	X	X	X
Lead surgically replaced	X	X	X	X	X	X	X	X	X	X	X	X	X
Lead surgically abandoned	X	X	X	X	X	X	X	X	X	X	X	X	X
Other lead-related surgery performed	X	X	X	X	X	X	X	X	X	X	X	X	X
Lead pacing polarity or mode reprogrammed*		X										X	
Lead electrically abandoned and pacing disabled	X	X										X	
Lead use continued based on medical judgment	X	X										X	

*Adverse events resolved by reprogramming of pacing polarity or pacing mode are only included in primary endpoint 1 analysis in cases of electrical or mechanical lead failure. Other adverse events, such as extracardiac stimulation, which are resolved by reprogramming are excluded.

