- Pneumothorax directly associated with the Sentus QP lead
- Cardiac perforation with or without tamponade caused by the Sentus QP lead
- Coronary sinus dissections directly caused by the Sentus QP lead (e.g., dissections caused by lead delivery device are excluded)

Finally, subject deaths resulting from a Sentus QP lead-related AE will be included in the primary endpoint analysis.

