11.3.4 Clinical Events Committee – MPP Sub-Study Events

The QP ExCELS Clinical Events Committee (CEC) described in Section 5.1 will adjudicate all adverse events that require additional invasive intervention to resolve which may be related to the MPP feature. These events include any software issues related to MPP programming or any adverse event that occurs while MPP is enabled and that may be attributed to the use of the MPP feature. The CEC will

^{††} Subjects enrolled at the 3-Month follow-up due to a prior HF hospitalization event will be followed at 6-months (90 ± 30 days post-MPP enrollment).

^{‡‡} Subjects enrolled at the 3-Month follow-up due to a prior HF hospitalization event will be seen at 9-months (180 ± 30 days post-MPP enrollment) and join the main QP ExCELS study at the 12-Month visit.

indicate whether the adverse event is related, possibly related, not related, or has an unknown relation to the MPP feature.

In addition, the CEC will adjudicate all deaths reported while participating in the MPP sub-study and classify each death as cardiovascular, vascular, non-cardiovascular/vascular, or unknown.

The CEC will adjudicate all reported protocol-defined hospitalizations while a subject is enrolled in the MPP sub-study. Hospitalization events will be classified as cardiovascular, vascular, non-cardiovascular/vascular, or unknown. Additionally, hospitalizations classified as cardiovascular will be further classified as a HF hospitalization, non-HF hospitalization, or unknown. Hospitalization events reported by the investigator as part of the initial responder classification for enrollment into the MPP sub-study will not be adjudicated by the CEC.

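### Section 5.1 gives the Clinical Events Committee no trigger for main-study deaths, so a death from a lead-related event may never be adjudicated or counted

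*Combined protocol and SAP*

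**What the plan says.** Section 6.6.2 closes its definition of endpoint 3 events with the statement that "subject deaths resulting from a Sentus QP lead-related AE will be included in the primary endpoint analysis". Section 6.6 makes the committee's judgement a condition for counting: events "for which the CEC determines the event is related or possibly related to the Sentus QP lead will be included", while those finally adjudicated as not related or of unknown relation are left out. Section 6.6 cites the endpoint 1 criteria when it states this rule. Section 5.1 gives the committee the same role for endpoint 3: "Final decision on inclusion of each adverse event in the primary endpoint 3 analysis according to the definition provided in Section 6.6.2".

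Section 5.1 also lists which site-reported events go to the committee:

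- Item 1: lead or generator events resolved by surgery.
- Item 2: "Adverse event related to clinical lead failure, electrical lead failure, or mechanical lead failure, regardless of action taken".
- Item 3: "Any major implant procedure related event that meets the criteria of a serious adverse event".
- Item 4: events of the MultiPole Pacing (MPP) sub-study.

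Protocol-defined events that meet none of these "will be included in the clinical report based on site-reported information".

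For a main-study death, Section 3.5.2.4 requires a Study Termination form, and an Adverse Event form only where one applies. The supporting documents must cover date, cause and circumstances, and "Whether death was device or procedure related". In the sub-study, by contrast, Section 11.3.4 states that "the CEC will adjudicate all deaths reported while participating in the MPP sub-study".

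**The concern.** A death is the most serious way a lead complication can end, and the endpoint definition counts it. To be counted, it must first reach the committee. The list in 5.1 is built on reported adverse events of certain types, and death in the main study is not one of them. Whether a death enters the process therefore depends on the site filing an adverse event of a listed type.

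The error has one direction. For deaths, a missed referral can remove a failure but cannot add one, so the complication-free rate can only be pushed up. In a single-arm comparison with a fixed performance goal, no control arm offsets this.

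**Working it through.** **1. Which fatal events have a route to the committee?** Setting 5.1 beside 6.6.2 and 3.5.2.4:

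| Fatal course in the main study | Counted under 6.6.2 if lead-related? | Route in 5.1 |
|---|---|---|
| After a lead event treated by surgery | Yes | Item 1 |
| After a reported clinical, electrical or mechanical lead failure | Yes | Item 2 |
| After a serious implant-procedure event (6.1.4 makes death a seriousness criterion) | Yes | Item 3 |
| Late dislodgement or lead-related thrombosis, no surgery, not classed as a lead failure | Yes, through the sentence on deaths | None stated |
| Death filed on a Study Termination form only | Yes, if lead-related | None stated |

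The last two rows are the gap.

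**2. Does the death then enter the endpoint 3 analysis?** Section 2.3.4 limits the analysis to successfully implanted subjects who completed the 60-month visit. Read literally, a subject who died earlier is excluded however the death is adjudicated, which conflicts with 6.6.2. For endpoint 1, Section 2.3.2 avoids the same problem by keeping subjects who had a qualifying event before the visit.

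The Kaplan-Meier analysis of 2.3.7 is affected either way. Section 2.5.4 censors subjects who exit before 5 years at study termination, and 3.5.3 sets that date at the date of death. An unadjudicated lead-related death is then a censored observation instead of a failure, in the curve that is compared with 92.5% for reporting to FDA.

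**3. The plan's own figures.** Inputs from 2.4.2: goal 92.5%, expected rate 94.75%, one-sided alpha 2.5%, power 80%, 11% exit per year.

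- n = [(1.960·√(0.925·0.075) + 0.842·√(0.9475·0.0525)) / 0.0225]² = 978.85, so 979. Reproduced.
- 979 / 0.89⁵ = 1753.2, so 1754. Reproduced.
- Exact binomial rule at n = 979: the test passes with at most 57 failures (lower 95% bound 92.52%) and fails with 58 (92.41%). Exact alpha is 2.4% and power 81.1%.

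**4. Size, under an assumption.** The documents give no rate of lead-related death. Suppose the true failure rate is exactly 7.5%, and d percentage points of it are lead-related deaths that go uncounted. The type I error is then P(F ≤ 57), where F is binomial with n = 979 and probability 0.075 − d.

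| d (percentage points) | Subjects of 979 | One-sided type I error |
|---|---|---|
| 0 | 0 | 2.4% |
| 0.1 | about 1 | 3.1% |
| 0.2 | about 2 | 4.0% |
| 0.3 | about 3 | 5.1% |
| 0.5 | about 5 | 8.1% |

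This table applies only once 2.3.4 is changed so that early deaths with an endpoint event are in the analysis set.

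**The case against.** A reader might infer that the site investigator alone decides whether a death counts. The documents do not support that. Items 1 to 3 already send many fatal lead and procedure events to the committee, which determines relatedness and has the final say on inclusion. The reporting threshold is also low: under 6.2 and 6.1.2 an event is reportable if a connection with the device cannot be excluded. Some loss of capture can qualify as clinical lead failure under Appendix A. Sponsor staff help to pre-select events, and study terminations are among the data that may be monitored centrally (9.1). What remains is narrower: the site's filing decides whether a death starts on that path, and no stated rule brings it back if it does not. Sponsor pre-selection sorts reported adverse events and is not independent.

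A reader might also set the distance between 57 allowed failures and the 51.4 expected (979 × 0.0525) beside the 775 planned early exits (1754 − 979), and conclude that about six missed deaths could plausibly change the result. That mixes two populations. The limit of 57 belongs to the 979 evaluable subjects, and the 775 are not among them. The exits also include withdrawals, explants, moves and changes of physician.

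The contrast with the sub-study is not in itself an inconsistency. Cardiovascular death is a component of the sub-study's primary endpoint, so every death there needs classification, whereas the main study counts only deaths from lead-related events.

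Two further limits stand. The committee's charter is not among the documents and may contain routing rules for deaths. And since unknown relation does not count under 6.6, some referred deaths would still end up outside the endpoint.

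**Conclusion.** The gap is real but limited. Section 5.1 does not require committee review of main-study deaths. A death filed only as a termination, or a fatal lead-related event outside items 1 to 3, therefore has no stated route to the body whose judgement is a condition for counting it. Any miss favours the device.

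The size cannot be fixed from the documents. Under the stated assumption of 0.1 to 0.5 percentage points uncounted, the one-sided type I error would be 3.1% to 8.1% in place of 2.4%. This holds only if 2.3.4 is reconciled with 6.6.2. As 2.3.4 now reads, earlier deaths are outside the endpoint 3 test in any case, and the practical effect of the missing trigger is on the 2.3.7 trend analysis. The point is worth correcting because the correction is small.

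**What to change.** 1. Add an item to the list in 5.1: any main-study death that is reported as device- or procedure-related, of unknown relation, sudden, or of undetermined cause. The committee classifies its relation to the Sentus QP lead from the documents required in 3.5.2.4.
2. Reconcile 2.3.4 with 6.6.2, so that the plan states whether a subject who dies of a lead-related event before the 60-month visit is in the endpoint 3 analysis set and counted as a failure. The wording of 2.3.2 for endpoint 1 is a ready model.
3. Apply the same adjudicated classification in the Kaplan-Meier analysis of 2.3.7, so that such a death is an event and not a censored observation.

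The cost is a modest number of extra cases for the existing committee, limited by the trigger. Section 3.5.2.4 accepts a death certificate, a signed report or medical records as alternatives, so the committee may need to request further source documents for some cases.
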